5.5.4 Follow-Up Inferential Analysis- Concomitant Vaccination Analysis

5.5.4.1 Incidence Rate Ratio (IRR) Estimation

The follow-up inferential analysis will only be performed for AEs for which a statistically significant elevated incidence rate ratio is observed from the primary analysis. This analysis will be implemented consistently with the primary analysis specified in Section 5.5.3.1, except the analysis will be conducted in two separate subgroups. One subgroup will include persons with an observed influenza vaccination *with any* concomitant (same-day) vaccination, and the other subgroup will include persons with influenza vaccination *without any* concomitant (same-day) vaccination. Where sufficiently powered, follow-up analyses may be performed by combinations of concomitant vaccines.

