Historically, adverse events (AEs) following influenza vaccination have been rare. Previous studies conducted in the U.S. and globally over the course of various influenza seasons largely support the safety profile of influenza vaccines showing no elevation in risk associated with several AEs following influenza vaccination.⁽⁴⁻⁹⁾ However, other studies have found associations between influenza vaccines and certain AEs including anaphylaxis, encephalitis or encephalomyelitis, Guillain Barré -Syndrome (GBS) and transverse myelitis.⁽¹⁰⁻¹⁶⁾ For some AEs, observed elevations in risks have largely been attributed to influenza infection.^(4, 17) There is also a potential for the risk of these AEs to be impacted by concomitant vaccination; evidence shows that vaccines such as COVID-19, hepatitis B, pneumococcal, tetanus, diphtheria, pertussis (Tdap), and Shingrix vaccines have displayed an association with some of these AEs when administered independently or concomitantly with other vaccines.⁽¹⁸⁻²¹⁾

For the 2022-23 season, there are multiple influenza vaccines available: Afluria Quadrivalent, Fluarix Quadrivalent, FluLaval Quadrivalent, Fluzone Quadrivalent, Flucelvax Quadrivalent, Flublok Quadrivalent, Fluzone High-Dose Quadrivalent, Fluad Quadrivalent, and FluMist Quadrivalent.⁽²²⁾ Of these vaccines, three are preferentially recommended by the Centers for Disease Control and Prevention (CDC) for use in people aged 65 years or older: Fluzone High-Dose Quadrivalent inactivated vaccine, Flublok Quadrivalent recombinant vaccine, and Fluad Quadrivalent adjuvanted vaccine.⁽³⁾

This document details the specifications for a self-controlled case series (SCCS) study in the U.S. to assess the incidence of select AEs (anaphylaxis, encephalitis or encephalomyelitis, GBS, and transverse myelitis) following administration of influenza vaccines approved for use during the 2022-2023 influenza season. These AEs were chosen because they have been studied in other vaccines. This study will be implemented in the Centers for Medicare & Medicaid (CMS) Medicare claims database among persons aged 65 years and older.

2. Objectives

The objective of this public health study is to assess the safety profile of influenza vaccines administered during the 2022-2023 influenza season in the U.S. population aged 65 years and older. The specific objectives are outlined below.

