- **Primary Objective:** To estimate the incidence rate of the following AEs: anaphylaxis, encephalitis or encephalomyelitis (including acute disseminated encephalomyelitis (ADEM)), GBS, and transverse myelitis after exposure to influenza vaccines in the risk interval, compared to the incidence rate of the AEs in the control interval. Assessment of AEs incidence rates will be performed for all influenza vaccine types combined together (overall), and for high-dose and adjuvanted vaccine groups separately. Vaccine groupings are presented in Table 3.
 - **Follow-Up Objective (if applicable):** If there is a statistically significant association in the primary analysis indicating a potentially increased rate of an AE in the risk compared to control interval, we will evaluate the potential contribution of concomitant (same-day) vaccination with at least one of five other vaccines to the elevated incidence rate for the given AE. The analysis for the specific outcome(s) with a statistically significant result will be stratified by concomitant vaccination status (influenza vaccination alone, and influenza vaccine *with any* same-day concomitant vaccination). Where sufficiently powered, follow-up analyses by combinations of concomitant vaccines may be performed.
 - Concomitant vaccines of interest are listed below.^{1(23, 24)} Table E1 can be referenced for associated vaccine code lists:
 - COVID-19 Bivalent (Pfizer-BioNTech, Moderna)
 - Pneumococcal (PCV15/20, PPSV23)
 - Hepatitis B
 - Tetanus (Tdap, tetanus, diphtheria (Td))
 - Shingrix

3. Data Sources

The study will be performed using the Medicare administrative claims database. The Medicare claims database includes well-defined longitudinal data that captures healthcare service utilization for millions of enrollees across multiple care settings including inpatient, outpatient-emergency department (OP-ED) and outpatient non-ED, professional services non-laboratory and laboratory, and pharmacy settings.

The Medicare Study will include CMS Medicare Shared System Data (SSD) to capture longitudinal healthcare information for persons aged 65 years and older in the study population. Medicare Fee-for-Service (FFS) Part A (inpatient) and Part B (outpatient and physician services) will be used to capture patient's vaccination history, healthcare services, health-related covariates, and diagnoses. Medicare

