5.4 Risk and Control Interval

5.4.1 Definition of Observation Period, Risk and Control Intervals

Specifications for AE-specific risk and control intervals are presented in Section 4.3.

Figure 1 presents a hypothetical example of the observation period for a person that experiences a qualifying GBS event following influenza vaccination. The observation period for this person will begin on the vaccination date and extend to 90 days following vaccination, including a 42-day risk interval, and a control interval extending from day 43 to day 90 following vaccination. Risk and control intervals for individuals will vary by AE and based on the presence of any censorship criteria. AE-specific risk and control interval specifications can be referenced in Section 4.3.

Figure 1. Hypothetical Example of Observation Period, Risk and Control Interval for Individual with a Qualifying GBS Event Following Influenza Vaccination

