5.5.1 Feasibility Analysis: Statistical Power and Sample Size

A power analysis will be performed to determine when the analyses can be conducted with sufficient sample size. This will be used to establish the data cut for the analysis, which will inform the study end date. The influenza vaccination uptake distribution in the 2022-2023 influenza season will first be obtained to ensure that the vaccination cutoff date (only vaccines prior to this cutoff will be eligible for inclusion in the study) is selected to capture at least 85% of vaccinations. Then, for each AE, vaccine cutoff date, and influenza vaccine group (reference Table 3), the outcome-specific data cut date will be estimated based on (i) the length of the observation window and (ii) the outcome-specific claims delay distribution with a 90% data completeness requirement. For each AE, vaccination cutoff date and influenza vaccine group, the expected number of events during the observation window will be estimated using the AE-specific historical background rates obtained from 2021. Finally, the minimum detectable IRR will be estimated, defined as the minimum effect size that can be detected in the study based on the expected sample size at 80% power and a two-sided alpha of 0.05. To determine if there is sufficient power to conduct the analysis, for each AE, vaccination cutoff date, and influenza vaccine group, we will identify comparable IRR estimates available in the literature. These will be compared against the minimum detectable IRR estimated in the power analysis, so that the data cut date/study end date used for the analysis can balance the trade-off between being able to detect reasonable differences in incident rates and the timely initiation of analyses.

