5.5.3 Primary Inferential Analysis

5.5.3.1 Incidence Rate Ratio (IRR) Estimation

The primary inferential analysis will evaluate the incidence rates of AEs following the influenza vaccines, comparing the rates of AEs in the risk and control intervals using a conditional Poisson regression model, conditioning on the total number of AEs observed for an individual patient in the observation period. This analysis will be restricted to the case population and conducted for each AE for influenza vaccines overall and by high-dose and adjuvanted vaccine groups.

The main primary analysis model will include a Farrington, seasonality and positive predictive value (PPV) adjustment (for AEs with PPVs available based on medical record review). The Farrington adjustment will be used to account for the reduced observation time that can occur from the occurrence of an event.⁽²⁷⁾ A separate analysis will be conducted including Farrington and PPV adjustments only, to evaluate the independent effect of the PPV adjustment excluding the seasonality adjustment. Another separate analysis will be performed including Farrington and seasonality adjustments only to evaluate

³ Covariate will be based on Health and Human Service (HHS) Region as specified on <https://www.hhs.gov/about/agencies/iea/regional-offices/region-1/index.html>

⁴ Beneficiaries' immunocompromised status will be determined based on a CBER-modified algorithm adapted from the Greenberg et al. algorithm, which was developed and validated to identify immunocompromised persons. Details on the algorithm can be found in Appendix 10.21.

the independent effect of the seasonality adjustment. The approach for the seasonality and PPV adjustments are specified in Section 5.5.5.

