5.5.5 Adjustments to Primary and Follow-Up Analyses

5.5.5.1 Seasonality Adjustment Analysis

Both the primary and follow-up analyses specified in Section 5.5.3 and 5.5.4 will include a seasonality adjustment, given that certain AEs included in the study demonstrate seasonal patterns in incident rates. This seasonality adjustment will adjust for changes in the baseline rate of AEs during different calendar months in the year. The baseline rate of AEs will be estimated from a similar population during the same calendar months in previous years, and subsequently included as an offset term in the regression model. For each AE, 2021 will be the comparator year used to adjust for changes in the baseline rate. Both 2020 and 2021 were considered as historical years for the seasonality adjustment; 2021 was selected as the adjustment period given that 2021 rates are more recent and thus likely more reflective of rates during the study period, and since the 2020 period has the potential to underestimate events due to changes in healthcare utilization during the early pandemic.⁽³³⁾

The Farrington and seasonality-adjusted model that will be used for the main primary and follow-up analyses is defined below.⁽²⁷⁾

$$\log(E(Y|X)) = \beta_1 * risk_interval + \log(w(t)) + \log(seasonal_risk) + strata(patient_id)$$

$$Y = AE$$

risk_interval = binary term indicating AE occurrence in risk interval

w(t) = Farrington adjusted weight

$$seasonal_risk = \frac{1}{IR_r * t} \sum_{m=1}^{12} (IR_m * t_m)$$

IR_m = daily incident rate for month *m*

IR_r = daily incident rate for reference month *r*

t_m = number of days in an interval in month *m*

$$t = \text{number of days in an interval or equivalently } t = \sum_{m=1}^{12} t_m$$

patient_id = term identifying the patient

In this model, the null and alternative hypotheses can be written as, respectively:

$$H_0: e^{\beta_1} = 1 \quad H_a: e^{\beta_1} \neq 1$$

Where e^{β_1} is the IRR for the AE in the risk interval compared to control interval adjusting for seasonality and curtailed observation time. A statistically significant coefficient at a pre-specified alpha level of 0.05 will indicate a statistically significant association between influenza vaccination and the AE.

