5.5.6 Attributable Risk (AR) Estimation

For the primary analyses and when follow-up analyses apply, the study will also estimate an adjusted AR statistic (per 100,000 vaccinations). The AR is the excess number of AE cases divided by the number of eligible beneficiaries (or eligible follow up dose-years). The number of excess AE cases due to the influenza vaccine will be derived directly from the conditional Poisson regression model, defined as the difference between the sum of the model fitted values (i.e., model predicted number of cases), and the sum of the expected cases (i.e., all observed time is treated as control time). The standard error (SE) of the AR is estimated by bootstrap resampling 10,000 times. For each iteration, this study will sample the beneficiaries with AE with replacement and repeat the AR calculation. The SE is calculated as the square root of the variance of the 10,000 AR values. AR estimates will be reported for each of the AEs for influenza vaccines overall, and by high-dose and adjuvanted vaccine groups separately.

6. Medical Record Review

For AEs without PPVs available from previous medical record review, medical record review may be considered if a significant elevation in incidence rates is detected from the study. The purpose of medical record review will be to evaluate the accuracy of the claims-based outcome definition(s) used. AE-specific PPVs and 95% CIs will be estimated to assess the probability of event misclassification based on the claims-based definitions used.

7. Ethical Evaluation

This public health surveillance activity is conducted as part of the FDA CBER BEST Initiative under the FDA Amendments Act of 2007. This study uses Medicare administrative claims data. The study involves no personal health information; no direct intervention on study participants; data used in this study is de-identified and anonymized before its use; the analysis is conducted in a Federal Information Security Management Act compliant environment; and the results are presented in aggregate.

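### The adjusted split by same-day co-vaccination depends on a significant pooled IRR, so a risk confined to co-vaccinees can be missed; the pooled AR is labelled as influenza vaccine alone

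*Protocol*

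**What the plan says.** The Follow-Up Objective in Protocol section 2 opens the co-vaccination analysis with a condition: "If there is a statistically significant association in the primary analysis indicating a potentially increased rate of an AE". Section 5.5.4.1 repeats it, saying that the analysis "will only be performed for AEs for which a statistically significant elevated incidence rate ratio is observed from the primary analysis". The two subgroups are influenza vaccine with any listed same-day vaccine and influenza vaccine without one.

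The analysis that acts as the trigger is "conducted for each AE for influenza vaccines overall and by high-dose and adjuvanted vaccine groups" (section 5.5.3.1). It pools over co-vaccination status, and no exclusion criterion in section 5.1 removes co-vaccinees. The test level is set in section 5.5.5.1: "A statistically significant coefficient at a pre-specified alpha level of 0.05 will indicate a statistically significant association". The model there contains a risk-interval term, the Farrington weight, a seasonal offset and patient strata. It has no term for other vaccines.

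Section 5.5.6 estimates an AR for the primary analyses, and for the follow-up analyses only when they apply. It states: "The number of excess AE cases due to the influenza vaccine will be derived directly from the conditional Poisson regression model".

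Three other places bear on the point:
- Section 1 says: "There is also a potential for the risk of these AEs to be impacted by concomitant vaccination".
- Section 5.5.2 summarises cases and unadjusted rates by risk and control interval, with concomitant vaccines as one of the breakdowns. This does not depend on significance.
- Section 5.1, inclusion criterion (i), requires Part D enrolment only if the co-vaccination analysis is run. The note to Table E1 explains that Shingrix, and some tetanus vaccine, is billed through Part D.

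**The concern.** A vaccine given on the same day has a post-vaccination window that coincides with that of the influenza vaccine. Comparing a person with himself or herself does not separate the two. The protocol recognises this possibility in its background, yet fixes adjusted estimates for influenza vaccine alone and for co-vaccinees only where the mixture of the two is already significantly raised.

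Two things are at stake. If an excess sits only among co-vaccinees, the pooled IRR is a weighted average that moves towards 1, and the more sensitive analysis for that pattern may not be run. In addition, the pooled AR is reported whatever its p-value, under wording that assigns all of it to influenza vaccine. The second point needs no assumed counts.

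**Working it through.** The protocol states no event count, co-vaccinated share, minimum detectable IRR or achieved power, so there is no figure of its own to reproduce first.

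**Inputs from the protocol**
- Intervals: "including a 42-day risk interval, and a control interval extending from day 43 to day 90 following vaccination" (section 5.4.1), so 42 and 48 days. Table 4 gives the same intervals for encephalitis and transverse myelitis. For anaphylaxis it gives days 0–1 and 3–16, so 2 and 14 days.
- Level: 0.05 (section 5.5.5.1). The feasibility analysis also works "at 80% power and a two-sided alpha of 0.05" (section 5.5.1).

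**Assumptions**
- B = 200 background cases, that is, cases expected if every IRR were 1 (also 100 and 400).
- Co-vaccinated share f = 25% (range 10% to 40%).
- IRR 1 for influenza vaccine alone and 2 for co-vaccinees.
- Farrington, seasonality and PPV adjustments are not modelled.

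**Dilution**

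Pooled IRR = (1 − f) × 1 + f × 2 = 0.75 + 0.50 = 1.25.

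**Expected cases (B = 200, f = 25%)**

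| Group | Risk interval | Control interval |
|---|---|---|
| Influenza alone | 150 × 42/90 = 70.0 | 150 × 48/90 = 80.0 |
| Co-vaccinated | 50 × 42/90 × 2 = 46.7 | 50 × 48/90 = 26.7 |
| Pooled | 116.7 | 106.7 |

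**Power by hand:** Φ(ln IRR / SE − 1.96), with SE = √(1/risk cases + 1/control cases)
- Pooled: SE = √(1/116.7 + 1/106.7) = 0.134; 0.223/0.134 = 1.67; power about 38%.
- Co-vaccinated stratum: SE = √(1/46.7 + 1/26.7) = 0.243; 0.693/0.243 = 2.86; power about 82%.
- Co-vaccinated stratum with Part D for half the cases (assumption): SE = √(1/23.3 + 1/13.3) = 0.343; 0.693/0.343 = 2.02; power about 52%.

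**Poisson simulation** (400,000 replicates per scenario, Wald test, z > 1.96)

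| Scenario (IRR 2 in co-vaccinees) | Trigger fires | Stratum significant |
|---|---|---|
| B = 200, f = 25% | 38% | 83% |
| B = 200, f = 10% | 10% | 43% |
| B = 200, f = 40% | 73% | 96% |
| B = 100, f = 25% | 21% | 53% |
| B = 400, f = 40% | 96% | over 99% |
| B = 200, f = 25%, half with Part D | 38% | 53% |

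In the first row the stratum is significant without the trigger firing in 46% of studies. With half the cases in Part D this falls to 26%.

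**More than one trigger test.** The primary analysis has three vaccine groups. With B = 200, f = 20% and assumed shares of 65% high-dose, 25% adjuvanted and 10% other, letting any group trigger raises the probability from 27% to 35%. The stratum is significant with no trigger in 43% of runs.

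**Anaphylaxis** (2/14 days, B = 200, f = 20%): trigger 17%, stratum 50%.

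**AR label.** In the table of expected cases, the pooled excess is 116.7 − 93.3 = 23.3 cases, where 93.3 = 200 × 42/90. All of it comes from co-vaccinees (46.7 − 23.3 = 23.3). Section 5.5.6 would nevertheless describe all of it as caused by influenza vaccine.

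**The case against.** The strongest reply is that the gate is deliberate. The follow-up objective is to explain a raised rate, and screening for co-vaccination signals is not an objective. That is a coherent choice, and it is why this is an improvement to the plan and not a contradiction within it. It does not deal with a signal hidden by pooling, nor with the AR wording.

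Four stronger readings are tempting, and the protocol does not support them.
- *The influenza-alone estimate will normally never be made, or a co-vaccinee risk always falls below the trigger.* Without counts or shares nobody can say so. With 400 cases and a 40% share the trigger fires in 96% of studies.
- *The co-vaccinated group goes unexamined.* Section 5.5.2 always gives its unadjusted rates by interval, so a crude contrast is visible. What is missing is the adjusted IRR, the AR, and the Part D requirement that secures capture of Shingrix and tetanus vaccines.
- *A null pooled result will be presented as reassurance about co-vaccination.* No section says this.
- *Strata examined after a chance trigger are inflated, so the gate should go.* The inflation is real, but removing the gate leaves the same cases and the same estimates in those studies. It is not a reason for the change.

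The Part D objection stands in part. It reduces the gain and must be built into the remedy. At 50% Part D coverage the stratum still has 53% power against 38% for the trigger.

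**Conclusion.** The concern holds in a limited form. As written, adjusted IRRs and ARs for influenza vaccine alone and for co-vaccinees exist only where the pooled IRR for that AE is significantly raised, so a risk confined to co-vaccinees can be missed by the inferential analysis. In the central scenario detection is 38% for the trigger against 83% for the stratum, or about 53% with half the cases in Part D. These figures rest on an assumed case count, co-vaccinated share, IRR and Part D coverage, and the gap closes as cases or the share grow. The attribution in section 5.5.6 goes further than the model allows, whatever those values are. The change is worth making because it is cheap and uses data the study already holds.

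**What to change.** 1. In sections 2 and 5.5.4.1, remove the significance condition for the two-stratum split. For all four AEs in the overall vaccine group, report the adjusted IRR and AR with 95% CI for influenza vaccine alone and for influenza vaccine with any listed same-day vaccine. Label them secondary and estimation-only.
2. State that these strata use the Part D-enrolled population of section 5.1, and show the pooled IRR in that population as well so that the three estimates are comparable.
3. Keep the significance trigger only for the breakdown by combinations of vaccines.
4. In section 5.5.6, describe the pooled AR as the excess following an influenza vaccination visit. Describe the influenza-alone AR as the excess after influenza vaccination without a listed same-day vaccine. That stratum should not be called purely influenza-caused either, because later doses of other vaccines do not censor follow-up (sections 5.1 and 5.4.1.1).

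Cost: wording, eight extra model fits (4 AEs × 2 strata) and the pooled refits in the Part D population, with fewer cases under Part D. If all IRRs are truly 1, and treating the estimates as independent, the chance of at least one falsely raised co-vaccinated stratum is 1 − 0.975⁴ = 9.6%. Over all eight estimates it is 1 − 0.975⁸ = 18%. This is why they should be estimation-only.

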5.5.5 Adjustments to Primary and Follow-Up Analyses

5.5.5.1 Seasonality Adjustment Analysis

Both the primary and follow-up analyses specified in Section 5.5.3 and 5.5.4 will include a seasonality adjustment, given that certain AEs included in the study demonstrate seasonal patterns in incident rates. This seasonality adjustment will adjust for changes in the baseline rate of AEs during different calendar months in the year. The baseline rate of AEs will be estimated from a similar population during the same calendar months in previous years, and subsequently included as an offset term in the regression model. For each AE, 2021 will be the comparator year used to adjust for changes in the baseline rate. Both 2020 and 2021 were considered as historical years for the seasonality adjustment; 2021 was selected as the adjustment period given that 2021 rates are more recent and thus likely more reflective of rates during the study period, and since the 2020 period has the potential to underestimate events due to changes in healthcare utilization during the early pandemic.⁽³³⁾

The Farrington and seasonality-adjusted model that will be used for the main primary and follow-up analyses is defined below.⁽²⁷⁾

$$\log(E(Y|X)) = \beta_1 * risk_interval + \log(w(t)) + \log(seasonal_risk) + strata(patient_id)$$

$$Y = AE$$

risk_interval = binary term indicating AE occurrence in risk interval

w(t) = Farrington adjusted weight

$$seasonal_risk = \frac{1}{IR_r * t} \sum_{m=1}^{12} (IR_m * t_m)$$

IR_m = daily incident rate for month *m*

IR_r = daily incident rate for reference month *r*

t_m = number of days in an interval in month *m*

$$t = \text{number of days in an interval or equivalently } t = \sum_{m=1}^{12} t_m$$

patient_id = term identifying the patient

In this model, the null and alternative hypotheses can be written as, respectively:

$$H_0: e^{\beta_1} = 1 \quad H_a: e^{\beta_1} \neq 1$$

Where e^{β_1} is the IRR for the AE in the risk interval compared to control interval adjusting for seasonality and curtailed observation time. A statistically significant coefficient at a pre-specified alpha level of 0.05 will indicate a statistically significant association between influenza vaccination and the AE.

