4.2 Exposure

The study will focus on influenza vaccinations approved for use during the 2022-2023 influenza season extending from August 1, 2022 to July 31, 2023.² Any beneficiary with a relevant vaccine product code between August 1, 2022 and November 12, 2022 (vaccination cutoff date) will be included in the study population. The vaccination cutoff date is the latest date in which influenza vaccines administered will be eligible for inclusion in the study. The rationale for the vaccination cutoff date is further described in Section 5.5.1. For persons eligible for inclusion in the study, only the incident vaccine administration observed during the study period will be included.

Table 3 presents a list of the product-specific administration codes⁽²²⁾ that will be used to identify influenza vaccine exposures by vaccine type and vaccine group. Analyses will be performed across influenza vaccines overall, and by individual vaccine groups (as referenced in Section 5.5). The study will specifically focus on codes recommended for use in persons aged 65 years and older. Current Procedural Terminology (CPT)/Healthcare Common Procedure Coding System (HCPCS) codes will be used to identify influenza vaccines administered. The following list will be expanded to include any additional influenza vaccine codes approved as of the study initiation date.

² Based on the effective dates for influenza vaccine codes specific to the 2022-2023 influenza season.

Table 3. 2022-2023 Influenza Vaccine Exposure Code List and Classifications

Code Type	Code	Vaccine Name	Vaccine Type			Vaccine Group
			Vaccine Classification		Abbreviated	
CPT	90662†	Fluzone High-Dose Quadrivalent (2022-2023)	Inactivated	High-dose	IIV4-HD	High-dose
CPT	90674	Flucelvax Quadrivalent (2022-2023)	Inactivated	Cell-cultured	ccIIV4	Other
CPT	90682†	Flublok Quadrivalent (2022-2023)	Recombinant	Recombinant	RIV4	Other
CPT	90686	Fluarix Quadrivalent (2022-2023)	Inactivated	Standard (split virus)	IIV4	Other
		Flulaval Quadrivalent (2022-2023)				Other
		Fluzone Quadrivalent (2022-2023)				Other
		Afluria Quadrivalent (2022-2023)				Other
CPT	90688	Fluzone Quadrivalent (2022-2023)	Inactivated	Standard (split virus)	IIV4	Other
		Afluria Quadrivalent (2022-2023)				Other
CPT	90694†	Fluad Quadrivalent (2022-2023)	Inactivated	Adjuvanted	aIIV4	Adjuvanted
CPT	90756	Flucelvax Quadrivalent (2022-2023)	Inactivated	Cell-cultured	ccIIV4	Other

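### The 2021 seasonality baseline does not exclude time shortly after influenza vaccination, so the offset can remove part of a recurring vaccine effect for GBS, encephalitis and transverse myelitis

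*Protocol*

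**What the plan says.** Protocol section 5.5.5.1 describes the offset in some detail. On the source of the rates it says "The baseline rate of AEs will be estimated from a similar population during the same calendar months in previous years", and on the year "For each AE, 2021 will be the comparator year used to adjust for changes in the baseline rate". The rates are monthly (the formula uses a "daily incident rate for month") and are "subsequently included as an offset term in the regression model", so their coefficient is fixed at 1. The reasons given for choosing 2021 are recency and the changed healthcare use of 2020. Influenza vaccination in the baseline year is not discussed.

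Section 5.5.3.1 places the offset in the main model: "The main primary analysis model will include a Farrington, seasonality and positive predictive value (PPV) adjustment". It also plans a version with the Farrington and PPV adjustments but no seasonality term. Table 5 lists PPVs for anaphylaxis and GBS only.

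For GBS, section 5.4.1 describes the observation period as "including a 42-day risk interval, and a control interval extending from day 43 to day 90 following vaccination". Table 4 gives the same intervals for encephalitis and transverse myelitis. For anaphylaxis it gives days 0–1 against days 3–16.

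Eligible vaccinations run from 1 August to 12 November 2022. Under section 5.5.1 the cutoff "is selected to capture at least 85% of vaccinations".

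**The concern.** Influenza vaccination is seasonal. In autumn 2021 part of any comparable Medicare population was inside its own 42-day post-vaccination window, in the same calendar months that supply most of the 2022 risk-interval days. If the vaccine raises the rate of an AE, and did so in 2021, the extra cases push up the 2021 rates for those months relative to the later months that supply the control intervals. The model reads that ratio as seasonality and divides it out.

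Section 4.3 says that the AEs were chosen for a potential association with influenza vaccines, partly from experience with earlier seasons, so an effect that recurs from year to year is within the protocol's own premise. The affected estimate matters: its significance triggers the concomitant-vaccination analysis (section 5.5.4.1) and possible medical record review for AEs without a PPV (section 6). The attributable risk is derived from the same type of model (section 5.5.6). The error runs toward missing a real signal in a safety study.

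**Working it through.** The protocol states no figure for the offset, no event count and no minimum detectable IRR, so there is no figure to reproduce. The check is the large-sample value of the section 5.5.5.1 model.

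**From the protocol:** intervals of 1–42 and 43–90 days, vaccination dates from 1 August to 12 November, monthly rates, fixed offset.

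**Assumed, because the protocol does not give them:**
- baseline coverage U of 40–60%;
- the uptake curve;
- a true IRR of 1, 1.5 or 2;
- the same effect and uptake in 2021 as in 2022;
- no true seasonality and no censoring;
- interval length carried elsewhere in the model.

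**Step 1, baseline.** With F_m the average share of vaccinees who are inside days 1–42 during month m:

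IR_m = 1 + U × F_m × (IRR − 1)

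Example: U = 0.5, IRR = 1.5, bell-shaped uptake peaking 15 October with SD 25 days (87% vaccinated by 12 November). In November F_m = 0.54, so IR_m = 1 + 0.5 × 0.54 × 0.5 = 1.135. The other months are 1.031 (September), 1.112 (October), 1.055 (December) and 1.007 (January). A correct baseline would be 1.000 throughout.

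**Step 2, offset.** Averaging these rates over each vaccinee's risk and control days, as in the seasonal_risk formula, gives a risk-to-control ratio of 1.041.

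**Step 3, estimate.** The conditional Poisson score equation gives an IRR of 1.441, which is close to 1.5 / 1.041. The share of the log IRR lost is 1 − ln(1.441)/ln(1.5) = 1 − 0.365/0.405 = 9.9%.

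**Range at U = 60% to 40%:**

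| Uptake curve | By 12 Nov | True 1.5 | True 2.0 | Log IRR lost |
|---|---|---|---|---|
| Bell, peak 1 Oct, SD 20 | 98% | 1.397–1.428 | 1.756–1.824 | 12–19% |
| Uniform, 1 Sep–12 Nov | 100% | 1.415–1.441 | 1.795–1.854 | 10–16% |
| Bell, peak 15 Oct, SD 25 | 87% | 1.430–1.452 | 1.834–1.881 | 8–13% |
| Bell, peak 5 Oct, SD 35 | 86% | 1.461–1.473 | 1.905–1.933 | 4.5–7% |

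All four curves meet the 85% requirement. At a true IRR of 1 every cell is 1.000. If the similar population meant vaccinees only (U = 100%), the bell curve peaking 15 October with SD 25 turns a true 1.5 into 1.39.

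**Anaphylaxis.** Days 0–1 and 3–16 mostly share the same monthly rate. True IRRs of 2, 5 and 20 are recovered within 0.3%.

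**With the remedy.** When the baseline uses only time outside days 1–42, and vaccinees and others share the same underlying rate, the offset is flat and 1.5 and 2.0 are recovered exactly.

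**The case against.** **Silence is not inclusion.** A reader might infer that the protocol does count post-vaccination time in the baseline. It does not say so. The similar population is undefined, and an SAP not shown here could restrict it. That stands, and it is why the point is worded as a missing exclusion. The protocol does, however, fix the year, the formula and the reasons for the choice, and followed as written nothing removes that time.

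**The effect must recur.** A reader might infer that every real effect is attenuated. Section 1 notes that the vaccines are reformulated each year, and a signal specific to 2022–2023 would not be reduced this way. That stands as a condition.

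**The size is assumption-driven.** That also stands. The loss of power cannot be fixed from the documents, because they give no case count. As an illustration with 300 cases and a true IRR of 1.4, power falls from 83% to 69% at a 15% loss of log IRR, but only to 79% at a 5% loss. With 500 cases and a 15% loss it goes from 96% to 89%.

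**An offset-free comparison is planned.** This is true for GBS, and section 5.5.2 reports unadjusted rates by interval for every AE. For encephalitis and transverse myelitis, the Farrington-and-PPV version arguably reduces to Farrington-only, but the text does not say so. The follow-up trigger still rests on the primary analysis.

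**The filter has its own bias.** Removing vaccinees' in-window time in autumn leaves a baseline weighted toward the unvaccinated in those months. Suppose 50% coverage, 60% of vaccinees in window in October, and a vaccinee rate 0.8 of others. The October rate is then (0.5 + 0.5 × 0.4 × 0.8)/(0.5 + 0.5 × 0.4) = 0.66/0.70 = 0.943, against 0.90 later, a false excess of about 5%. Averaged over whole intervals and the curves above, the IRR shifts by about 0.6–2%, also at a true IRR of 1, where the planned model has no bias. This stands as a real cost. It is smaller than the 2–7% attenuation of the IRR that the filter removes at a true 1.5 (1.47/1.5 to 1.40/1.5).

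**Conclusion.** The point holds in conditional form. If the 2021 rates keep post-vaccination risk time and the vaccine effect was also present in 2021, the main primary IRR for GBS, encephalitis and transverse myelitis is pulled part of the way toward 1. Under assumed coverage of 40–60% and the uptake curves shown, about 4–19% of the log IRR is lost: a true 1.5 becomes 1.40–1.47 and a true 2.0 becomes 1.76–1.93. Type I error is not inflated, and anaphylaxis is essentially unaffected.

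Two stronger readings are not supported. The attenuation does not erase a signal or invalidate the primary analysis, so this is a worthwhile correction rather than a fatal defect. Nor do the documents or these calculations give grounds for also excluding time after the other listed vaccines from the baseline.

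**What to change.** 1. In section 5.5.5.1, define the similar population and state that IR_m is computed from person-time outside days 1–42 after influenza vaccination for GBS, encephalitis and transverse myelitis. For anaphylaxis the corresponding exclusion makes practically no difference.
2. In section 5.5.3.1, name a Farrington-only model, with no seasonality offset, to be reported for all four AEs. The size of the seasonal correction is then visible also where no PPV exists.
3. As a check on composition, standardise the monthly baseline rates to a fixed vaccinated/unvaccinated mix and report whether the IRR moves.

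The cost is a person-time filter on the 2021 rates, slightly fewer baseline events per month, one extra model per AE, and the compositional shift that step 3 is there to check. No new data source is needed, since vaccination dates come from the same claims.
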